12.3.3 Injection Site Tolerability Assessment

Injection site tolerability assessments will be performed as described in Appendix I.

12.4 Time Windows for Visits

Vital signs will be performed within ±15 minutes of the scheduled time.

The time window for Visits 3 and 7 is ±2 hours.

The time window for Visits 4, 5, 6, 8, 9 and 10 is ± 2 days.

The time window for Visit 11 is ±2 weeks.

12.5 Safety Monitoring Board and Safety Data Review Meetings

Both cohorts will incorporate sentinel dosing of 2 subjects in each cohort for the primary dose only: 1 on active treatment and 1 on placebo. No further subjects in that cohort will be

dosed until 24 hours after dosing the second subject, provided that there are no serious or unexplained safety issues as determined by the Investigator.

The decision to proceed with administration of the primary dose the subsequent cohort will be made as follows:

- It is intended that safety will be assessed after at least 24 evaluable subjects in cohort 1 (sentinel and main dose groups) have completed Visit 4 (Day 8), at which point the decision will be made to proceed with administration of the primary dose in cohort 2.

At least 24 evaluable subjects are required to complete through to visit 4 in cohort 1, in order to provide sufficient data for a decision to dose escalate. If the required number of evaluable subjects is not obtained in cohort 1, then the safety review committee (SRC) must decide whether there is enough information present to make a decision or whether further subjects should replace the dropped subjects or if sufficient information exists to determine if the dosing of cohort 2 is appropriate. The decision of the safety monitoring board and the output of the safety review must be clearly documented after the meeting.

The following safety data will be reviewed:

- Clinical Laboratory Tests
- Vital signs
- Assessment of injection site reactions
- AEs

The SRC will include at least two voting members - the Principal Investigator and Sponsor's Medical Monitor. If a voting member is unable to attend a Safety Data Review Meeting, a designated back-up can attend on their behalf and act as a voting member. Designated back-ups must be agreed and documented in advance. Non-voting members may also be part of the SRC.

The SRC will meet in person or by teleconference at scheduled Safety Data Review Meetings at which the safety data will be reviewed. A summary of safety data will be provided for review prior to these meetings for the SRC to review.

After review and discussion of all the data, the decision will be made on dose escalation and documented by signature of a Dose Escalation Approval Form by the voting members of the SRC. Minutes documenting the main points discussed and decisions made regarding dose escalation will be produced. The minutes will be agreed by all parties and filed in the site Trial Master File.

Progression to the next higher dose level will be stopped if any of the study stopping criteria are met as described in Section 12.7. Individual subjects will be discontinued from the study if they meet any of the individual subject stopping criteria as described in Section 12.6.

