24 HOUR SPONSOR MEDICAL MONITOR

[REDACTED]

SAFETY REPORTING

[REDACTED]

SAFETY LABORATORIES

[REDACTED]

STATISTICS

[REDACTED]

ANALYSIS OF PHARMACODYNAMIC BLOOD SAMPLES

[REDACTED]

And

[REDACTED]

[REDACTED]

	
 • Geometric mean fold increase in antibody concentration. • Seroconversion rate (proportion of subjects with fold increase above threshold at any time post vaccination). • Proportion of subjects achieving antibody concentrations above specific thresholds at Days 29 & 85 (these will be 2, 4, 8 µg/mL). This will provide an assessment of the immune response to the first and second doses. 									
Study Design:	
This is a Phase I, randomised, double-blind, placebo-controlled, parallel group, single centre study.
 
There will be 2 cohorts of 30 subjects. Cohort 1 will receive two 0.5 mL injections, 4 weeks apart, each consisting of 25 µg of GBS-NN and 25 µg of GBS-NN2 (24 subjects) or placebo (6 subjects). Cohort 2 (30 subjects) will receive two 0.5 mL injections, 4 weeks apart, each consisting of 50 µg of GBS-NN and 50 µg of GBS-NN2 (24 subjects) or placebo (6 Subjects). All vaccines will be adsorbed to 500 µg Al3+ as Alhydrogel®.
 
Safety will be assessed after all subjects have completed Visit 4 (Day 8) for Cohort 1, at which point the decision will be made as to whether proceeding with administration of the doses in cohort 2 is appropriate.
									
Study Duration:	Study start is defined as check-in to the study unit on Day 1. Each individual subject will be involved in the study for approximately 12 weeks (excluding the 28 day screening period and the 6 month safety follow up).									
Study Population:	60 healthy female subjects aged 18 to 40 will be randomised into 2 cohorts of 30 subjects.									
Investigational Medicinal Product and mode of administration	
GBS-NN/NN2 vaccine will be supplied [REDACTED]
 
The placebo vaccine will contain Alhydrogel® mixed with sterile dilution buffer.
									

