6.3 Risk/Benefit Assessment

Antibodies against the full-length Rib, AlphaC, Alp1, Alp2 and Alp3 proteins, from which the GBS-NN and GBS-NN2 are derived to make up the vaccine antigens, naturally occur in women exposed to GBS, and such antibodies are efficiently transferred to the unborn child *in-utero*. Many adults and new-born infants have, therefore, already been naturally exposed to the proteins from which the antigen is derived and to antibodies against these proteins, and no side effects have been attributed as a consequence of such exposure in humans.

[REDACTED]

[REDACTED]. The maximum human dose will be 50 µg, which if administered to a 60 kg woman would equate to 0.83 µg/kg giving a safety margin of at least 60-fold.

The planned excipients in the vaccine formulation are also all well-known from other vaccines, and no novel or non-tested components are used. The proteins in the vaccine are adsorbed with a known adjuvant, Alhydrogel®, (0.5 mg of Al³⁺ per dose), corresponding to the dose used in many other commercial vaccines.

This is a new investigational product; therefore, there are currently no expected AEs related to the product. However, following injection of GBS-NN alone, approximately 30% of the subjects in the study experienced mild pain. Pain post-injection that is worse than mild would be considered to be unexpected. It is not anticipated that adding the two additional antigenic proteins, to GBS-NN, bound to Alum will significantly alter the safety profile. The Investigator is responsible for reporting adverse events (AEs) that occur during the course of the study. Serious adverse reactions that are deemed to be related to the investigational product in the proposed study will be reported as suspected unexpected serious adverse events (SUSAR).

GBS-NN/NN2, like other protein-based vaccines, may theoretically be associated with a transient febrile reaction (body temperature greater than 38.0°C but not greater than 38.7°C) following vaccination. Immune complex-mediated reactions are unlikely given the recombinant nature of GBS-NN/NN2, however, it is still possible that hypersensitivity may occur.

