9.3 Planned Sample Size

60 healthy female subjects aged 18 to 40 will be randomised into 2 cohorts of 30 subjects.

At least 24 evaluable subjects in cohort 1 will be required to attend through to visit 4 in order to provide sufficient data for a decision to dose escalate in cohort 2. If the required number of evaluable subjects are not obtained in a cohort, then the safety review committee (SRC) must decide whether there is enough safety information available to make a decision or whether further subjects should replace the dropped subjects or if sufficient information exists to determine if the dosing of cohort 2 is appropriate.

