9.4 Allocation of Randomisation Numbers

Subjects will be allocated to treatment groups according to a randomisation code produced by ████████ using the PROC PLAN procedure of SAS® version 9.3.

Subjects will be numbered sequentially from 001 (i.e. 001, 002 etc.). Replacement subjects will be assigned the same randomisation as the subject they are replacing, however, 100 will be added to the number (i.e. 101 would replace 001 etc.).

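### The synopsis holds the dose-doubling decision until all cohort 1 women complete Visit 4, but 9.3 and 12.5 allow it at 24 evaluable women of either arm, of whom as few as 18 may be vaccinees

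*Combined protocol and SAP*

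**What the plan says.** The synopsis (Study Design) gives the escalation point as "Safety will be assessed after all subjects have completed Visit 4 (Day 8) for Cohort 1". Section 9.3 reads "At least 24 evaluable subjects in cohort 1 will be required to attend through to visit 4", and 12.5 has "safety will be assessed after at least 24 evaluable subjects in cohort 1 (sentinel and main dose groups) have completed Visit 4 (Day 8". Neither section names an arm or defines evaluable. The sentinel pair that 12.5 counts is one vaccinee and one placebo woman.

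Cohort 1 receives "25 µg of GBS-NN and 25 µg of GBS-NN2 (24 subjects) or placebo (6 subjects", so it has 30 women. Cohort 2 doubles each protein to 50 µg.

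Both the synopsis (Treatment Schedule) and 12.2 send the reader to 12.5 for the decision on cohort 2. If 24 evaluable women are not obtained, 9.3 and 12.5 leave it to the safety review committee (SRC) to judge whether the data suffice or dropped women should be replaced. On replacement, 9.4 states: "Replacement subjects will be assigned the same randomisation as the subject they are replacing".

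Section 12.7 sets three of its criteria at more than 20% of a cohort's subjects, alongside a sentinel trigger in each. Section 12.5 makes the criteria binding: "Progression to the next higher dose level will be stopped if any of the study stopping criteria are met".

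**The concern.** The decision at stake is whether to double the dose of a new combination in healthy women. The synopsis and the operative sections describe different amounts of evidence for it. Under 12.5 the review may take place at the 24th completer, with nobody having dropped out and six women already dosed but not yet seen at Day 8. Visit 4 is the first visit after vaccination with safety bloods and urinalysis, so for those six the review would have no post-dose laboratory data.

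The number 24 also says less than it seems to, because placebo women count towards it. Only vaccinees inform the safety of the 25 µg dose. The trial is double-blind, and 12.5 does not say that the committee is told how many of the completers were vaccinated.

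**Working it through.** The plan gives no derivation for 24 (no target rate, confidence level or dropout allowance), so there is no stated calculation to reproduce. The counts agree: 24 + 6 = 30 per cohort, and 2 × 30 = 60.

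**Vaccinees behind the decision.** If m of the 30 women lack Visit 4 data and all m are vaccinees, 24 − m vaccinees remain. With zero events among n vaccinees, the one-sided 95% upper limit on the event rate is 1 − 0.05^(1/n).

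| Women without Visit 4 data (m) | Women with data | Fewest vaccinees (n) | Zero-event upper limit |
|---|---|---|---|
| 0 | 30 | 24 | 11.7% |
| 2 | 28 | 22 | 12.7% |
| 4 | 26 | 20 | 13.9% |
| 6 | 24 | 18 | 15.3% |

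For an event with an assumed true rate of 10%, the chance of seeing at least one is 1 − 0.9^24 = 0.920 with 24 vaccinees and 1 − 0.9^18 = 0.850 with 18.

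**How likely the worst case is.** If the six missing women are a random six of the 30, the vaccinees among the 24 completers follow a hypergeometric distribution. The mean is 24 × 24/30 = 19.2. The chance of exactly 18 is C(24,18)/C(30,24) = 134,596/593,775 = 22.7%.

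**Length of the wait.** Visit 4 falls 7 days after the first dose. Section 12.4 states "The time window for Visits 4, 5, 6, 8, 9 and 10 is ± 2 days", while 12.2 allows 1 day. The latest in-window visit is therefore 7 + 2 = 9 days after the last cohort 1 first dose, or 8 days under 12.2. The delay beyond the 24th completer depends on the enrolment rate, which is not stated.

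**The 20% trigger in 12.7.** 20% of 30 is 6.0, so the first count above it is 7. If all seven are vaccinees, that is 7/24 = 29.2% of the vaccine arm. A count of 5 would be 5/24 = 20.8% of vaccinees and 5/30 = 16.7% of the cohort. For persistent fever, suppose a true rate p in vaccinees, no placebo events, and one vaccinated sentinel whose event triggers alone. The criterion is met with probability p + (1 − p) × P(Bin(23, p) ≥ k). At an assumed p = 5% this is 5.5% for k = 5 and 5.0% for k = 7. At p = 10% it is 16.6% and 10.5%. For comparison, the rule of two severe related reactions is met among 24 vaccinees with probability 0.708 at a 10% severe rate and 0.991 at 25%.

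**The case against.** The strongest reply is that the protocol settles precedence. A reader might infer from the synopsis that staff hold two competing rules; the documents do not support that, because the synopsis itself and 12.2 both defer to 12.5. This stands. It leaves a synopsis sentence that contradicts the governing section, and the rule that governs is the weaker of the two.

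Second, 24 may be meant only as an allowance for dropouts, since both 9.3 and 12.5 go on to speak of replacing dropped subjects. That is a fair account of intent, and the documents do not show that the sponsor plans to review early. The operative sentence nevertheless permits it.

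Third, 24 is also the size of the vaccine arm, so a reader might take it to mean 24 vaccinees. No arm is named, and the sentinel pair that is counted includes a placebo woman.

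Fourth, women short of Day 8 are not unobserved. They have vital signs at 2 and 4 hours and the 24-hour visit, they are told to report adverse events promptly, and the committee discusses all data before signing. This stands and limits the harm: the upper limits above concern what is first seen by Day 8, not all safety information.

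A stronger reading of 12.7 is also tempting: that its 20% has no defined denominator and is spoiled by placebo women. The documents do not support it. A cohort is 30 women, so the literal count is 7, and counting both arms suits a rule applied blind. Other 12.7 triggers (one sentinel reaction, one related SAE, two severe related reactions) usually act first. What remains is mainly persistent fever not graded severe, and 6.3 says only that the vaccine "may theoretically be associated with a transient febrile reaction".

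**Conclusion.** The inconsistency is real and should be corrected. As 12.5 is written, the decision can rest on 18 to 24 vaccinees with Day 8 data, where the synopsis implies all 24. At the bottom of that range the zero-event upper limit is 15.3% instead of 11.7%. The 18 requires that all six missing women be vaccinees; the 19.2 assumes that they are a random six. Neither is an absolute minimum, because the SRC may also decide with fewer than 24 evaluable women.

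The loss is moderate and its remedy is cheap. A reader might infer that replacement under 9.4 restores the vaccinee count in every case. It does not: if six vaccinees are lost, 24 evaluable women remain, the floor is met and no replacement is called for.

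The 12.7 point is minor. A fixed count would remove any doubt about a rule that stops progression. The fever rates used to size it are assumptions without support in the documents.

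**What to change.** Put one rule in the synopsis, 9.3 and 12.5: *Safety will be assessed after all dosed cohort 1 subjects have completed Visit 4 (Day 8), have withdrawn, or have passed the end of the Visit 4 window.* The last clause prevents a woman who misses Visit 4 without withdrawing from holding up the review indefinitely. Keep 24 evaluable as the floor below which the SRC decides on sufficiency or replacement, and recognise that it does not secure 24 vaccinees if the losses are mostly in that arm.

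The cost is wording in three places and a wait ending no later than 9 days after the last cohort 1 first dose.

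As a minor edit, replace the 20% in the three 12.7 criteria with a fixed count. Seven or more keeps the literal rule for a 30-woman cohort. A lower count such as 5 would be a more sensitive trigger, but that is a design choice for the sponsor, not a correction.

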12.6 Individual Subject Stopping Criteria

Subjects who meet one or more of the following stopping criteria will receive no further doses of the study vaccine but will be followed up for safety:

- Severe injection site reaction, see Appendix I
- Severe systemic reaction, e.g. anaphylaxis, see section 14.2.1
- Persistent febrile reaction ($\geq 38.5^{\circ}\text{C}$ for ≥ 12 hours) at the Investigator's discretion
- SAE related to the study agent

The medical safety of the subject is of paramount importance when discussing study continuation.

12.7 Study Stopping Criteria

A Safety Review Meeting will be convened to determine the progression of the study if any of the following scenarios occur:

- If one of the sentinel group or more than 20% of the subjects in a cohort experience a severe site reaction related to the GBS-NN/NN2 vaccine (study agent).
- If one of the sentinel group or more than 20% of the subjects in a cohort experience a severe systemic reaction related to the study agent.
- If one of the sentinel group or more than 20% of the subjects in a cohort experience a persistent febrile reaction ($>38.5^{\circ}\text{C}$ for ≥ 12 hours) related to (study agent).
- If one or more subjects experience a SAE related to the study agent.
- If two or more subjects in the same cohort, experience 'severe' non-serious adverse reactions (i.e. severe non-serious adverse events, independent of system-organ-class, considered at least possibly related, to the IMP administration).

13. PHARMACODYNAMIC ANALYSIS AND ASSESSMENTS

13.1 Pharmacodynamic blood sample – antibody response

Each blood sample will be approximately 20 mL in volume, to yield approximately 10 mL of sera. The sera will be divided into aliquots, as described in the laboratory manual. Seven samples will be collected during the study which represents approximately 140 mL of blood.

The total blood volume taken over the study will be approximately 300 mL, which represents seven of approximately 20 mL pharmacodynamic samples, two of approximately 40 mL PBMC's and seven of approximately 9 mL clinical laboratory blood samples.

Pharmacodynamic samples will be collected at the following timepoints; Day 1, Day 15, Day 29, Day 43, Day 57, Day 85 and Day 210

Detailed processing instructions will be included in a separate lab manual.

[REDACTED]

Serum samples for PD antibody response analysis will be performed at [REDACTED] at [REDACTED] and [REDACTED]

Serum samples will be assayed in a validated ELISA to measure the concentrations of IgG specific for GBS-NN and GBS-NN2. Raw data from the assay will be inspected by the QC/QA scientists at the analytical lab to identify any samples which give unexpected results based on the normal kinetics of IgG induction following vaccination. Such unexpected values may indicate a problem with sample identification or with the assay performance. Potentially anomalous results will be discussed with the sponsor, without revealing the identity of the subjects, and if necessary samples will be re-analysed and corrected if the result fits with expectation. If the re-analysis returns essentially the same result a decision will be taken on whether to exclude the samples from the IG population analysis. Prior to formal statistical analysis of the results a standard test for outliers (e.g. the ROUT function in Graphpad Prism or equivalent) will be performed and any data points identified will be excluded from the analysis. In parallel the analysis will be performed on all data points including outliers to reveal the magnitude of the effect of excluding them.

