15.2 Studied populations for each study part

The following populations will be taken into account for each study part:

- **Randomized Set (RAN):** All included subjects who are randomized at V2 to one of the two cohorts;
- **Safety Set (SAF):** All subjects from the SAF set who receive at least one dose of the study vaccine (or placebo) will be taken into account in the description of the population (demographic or baseline characteristics);
- **Immunogenicity Set (IG):** The subset of subjects from the SAF set who will receive at least one dose of the study vaccine (or placebo) with available pre- and post-vaccination titres.
- **Per Protocol Set (PP):** All subjects from the IG set who receive both doses of the study vaccine (or placebo) and provide evaluable samples for analysis of the IgG antibody response to the GBS-NN/NN2 vaccine at Day 85 (most important immunological endpoint) and do not violate the protocol.

The safety analyses will be performed on the SAF set. The immunological analyses will be performed on the IG set. The most important immunological endpoint (immune response on Day 85) will also be performed on the PP set if the number of subjects in the PP set differs by more than 5% from the number of subjects in the IG set.

Missing or incomplete data will not be replaced, unless otherwise specified (example: values strictly under the LLOQ for immunogenicity data).

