15.4.3 Secondary Endpoints (Immunological Endpoints)

The secondary objectives are:

- To evaluate the IgG antibody response to the GBS-NN/NN2 vaccine at Day 85 (most important immunological endpoint).
- To assess whether pre-existing antibody levels affect the vaccine-induced antibody response.

Immunological parameters measured to evaluate objectives

In order to evaluate these objectives, GBS-NN and GBS-NN2 specific IgG concentrations will be determined by ELISA against a reference standard human antibody preparation of known concentration as described in the laboratory protocol and used to derive the following parameters for each subject:

- Antibody concentrations specific for GBS-NN and GBS-NN2 at each sample point ($\mu\text{g/mL}$)
- Fold increases over pre-immunisation level (Day 1) in antibody concentrations at each sample point (ratio)

Specific Endpoints calculated from immunological parameters

These parameters will be used to derive the following endpoints at all time-points according to the treatment group:

- Geometric mean antibody concentrations specific for GBS-NN and GBS-NN2 in $\mu\text{g/mL}$ (with 95% CI).
- Geometric mean fold increase in antibody concentration (with 95% CI).
 - Seroconversion rate (proportion of subjects with fold increase above threshold at any time point post vaccination up to Day 85).
- Proportion of subjects achieving antibody concentrations above specific thresholds at Days 29 & 85 (these will be 2, 4, 8 $\mu\text{g/mL}$). This will provide an assessment of the immune response to the first and second doses.

The most important immunological end point will be the values of these end points at Day85, 12weeks after the administration of the first dose of vaccine.

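### Section 13.1 lets the IgG values themselves, rather than documented faults, decide which results enter the immunological analysis

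*Combined protocol and SAP*

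**What the plan says.** Section 13.1 describes three steps between the ELISA result and the analysis.

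1. **Kinetics query.** Laboratory QC/QA staff inspect the raw data "to identify any samples which give unexpected results based on the normal kinetics of IgG induction following vaccination". The reason given is sound: "Such unexpected values may indicate a problem with sample identification or with the assay performance". Queried results are discussed with the sponsor with subject identity withheld. If necessary, "samples will be re-analysed and corrected if the result fits with expectation".
2. **Confirmed values.** "If the re-analysis returns essentially the same result a decision will be taken on whether to exclude the samples from the IG population analysis". No criterion or decision-maker is named.
3. **Outlier test.** A standard test (ROUT in GraphPad Prism is the example, or an equivalent) "will be performed and any data points identified will be excluded from the analysis". The scale, threshold and grouping are not stated. The section then adds: "In parallel the analysis will be performed on all data points including outliers to reveal the magnitude of the effect of excluding them".

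Section 15.2 assigns the immunological analyses to the IG set: subjects from the safety set with at least one dose and "with available pre- and post-vaccination titres". It mentions no exclusion based on the size of a result. Section 15.4.3 lists the endpoints built on these values: geometric mean concentration and fold increase with 95% intervals, seroconversion rate, and the proportions above 2, 4 and 8 µg/mL. It adds: "The most important immunological end point will be the values of these end points at Day85".

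**The concern.** Each step is settled by how the number looks. A repeat is accepted because it agrees with what was expected. A reproduced value can be removed although the repeat has weakened the assay-fault explanation. An outlier flag leads to exclusion without any enquiry into cause.

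Antibody responses to a vaccine are skewed, and some people respond very strongly or hardly at all. Those are the subjects such rules pick out, and they belong in the estimate. Removing high responders lowers the geometric mean. Removing non-responders raises it, along with the seroconversion and threshold rates. Either way the remaining data look less variable than they are, so the intervals are too narrow.

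The parallel run is a real safeguard for step 3, but its wording ties it to the outlier test. Nothing says it brings back a value replaced or dropped in steps 1 and 2. One secondary objective asks whether pre-existing antibody alters the response. Subjects with high baseline antibody could plausibly show unusual kinetics, so step 1 might filter out the variation that objective studies; that is an inference, not something the plan states.

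**Working it through.** **Inputs.** From the documents: 24 active and 6 placebo subjects per cohort (synopsis, Study Design); geometric means with 95% intervals (15.1.2, 15.4.3). The documents give no SD, non-responder rate, test scale or threshold, and no power calculation, so there is no figure of the plan's own to reproduce. Assumed instead: lognormal IgG; log10 SD 0.3, 0.4, 0.5 and 0.6; a ROUT-type rule with Q = 1%; no faulty data.

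**Rule simulated** (n = 24, 4,000 to 6,000 groups per setting).
- Robust centre m (Lorentzian weights).
- Scale s = 68.27th percentile of |x − m|, times n/(n − 1).
- p = 2·P(T with n − 1 df > |x − m|/s).
- Order the p-values and flag those up to the largest i with p(i) ≤ Q·i/n, limited to the largest 30% of residuals.

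**Why the scale matters.** At log10 SD 0.4, a value 2 SD above the centre is 10^0.8 = 6.3 times the geometric mean, and one 2 SD below is 1/6.3 = 0.16 times it. On the raw scale these lie 5.3 units above and 0.84 units below, so a raw-scale test flags high values.

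**Outlier step: results after exclusion.** Ratios are geometric mean after exclusion over geometric mean of all data.

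| log10 SD | 0.3 | 0.4 | 0.5 | 0.6 |
|---|---|---|---|---|
| Raw scale, no non-responders: ratio | 0.94 | 0.88 | 0.81 | 0.73 |
| Same: 95% interval coverage | 88% | 82% | 77% | 71% |
| Log scale, no non-responders: ratio | 1.00 | 1.00 | 1.00 | 1.00 |
| Log scale, 1 of 24 non-responders: ratio | 1.11 | 1.06 | 1.03 | 1.02 |
| Log scale, 2 of 24: ratio | 1.22 | 1.10 | 1.05 | 1.02 |
| Log scale, 3 of 24: ratio | 1.29 | 1.11 | 1.05 | 1.03 |
| Same (3 of 24): share of their values removed | 55% | 20% | 8% | 4% |

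Non-responders are placed 1.5 log10 lower (10^1.5 = 32-fold). In the log-scale runs without them, about 1% to 2% of groups lose a value and coverage stays at 94% to 95%.

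A separate run with a median centre gave the same picture. On the raw scale, at SD 0.3, 0.45 and 0.6, 54%, 83% and 94% of groups lost at least one genuine value, every one of them high; coverage was 89%, 81% and 73%. On the log scale at SD 0.3, with 5% to 15% low responders 1.2 log10 lower, the geometric mean rose by about 5% to 7% and coverage fell to 82% to 89%, against about 94% with all values kept.

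**Kinetics step, by arithmetic.** Suppose 21 of 24 subjects exceed a threshold (a hypothetical count). Exact 95% intervals in brackets:
- all kept: 21/24 = 87.5% (67.6% to 97.3%);
- one confirmed non-responder dropped: 21/23 = 91.3% (72.0% to 98.9%);
- two dropped: 21/22 = 95.5% (77.2% to 99.9%).

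On the wording of 13.1, the parallel run need not reveal this shift.

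**The case against.** The strongest reply has five parts.

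- **Both runs are produced.** The natural reading is that the excluded run leads and the all-data run is the sensitivity analysis, so a reader can see the effect of the outlier test. This limits the harm of step 3. It does not reach steps 1 and 2, and on that reading the leading run is the one that can be biased.
- **The raw scale is unlikely.** Geometric means imply log-scale work, and there the test does almost nothing when there are no non-responders. That is fair, but 13.1 does not state the scale, and the choice decides both the size and the direction of the effect.
- **The non-responder figures depend on the assumed deficit.** They do. At SD 0.3 with 3 of 24, the rise of 29% at a 1.5 log10 deficit becomes about 11% at 1.2 and 5% at 1.0; at SD 0.5 the last two are about 2% and 1%.
- **The study is double-blind** (10.5), and the randomisation list is restricted to unblinded personnel (10.3). This stands as general protection. Section 13.1 itself mentions only subject identity, and the timing of unblinding relative to these decisions is not given.
- **Section 15.2 defines subjects, not data points, and detail may sit in the SAP, the laboratory manual or redacted text.** Both points are reasonable: there is no outright contradiction with 15.2, and repeat-testing criteria may exist elsewhere. But 13.1 already states the exclusion as a rule, so added detail would have to reverse it rather than complete it.

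**Conclusion.** The concern holds and should be fixed. As written, 13.1 permits genuine IgG results to be replaced or removed because of their size, and no sentence says which of the two runs is the reported result.

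For the outlier step, the effect on a 24-subject geometric mean runs from nil to a fall of about 27% or a rise of about 29%. Which applies depends on the unstated scale and on assumed values for the SD, the number of non-responders and their deficit. These figures are illustrations, not predictions for this trial. The kinetics step cannot be sized without knowing how many values it would touch.

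The reach is limited. Safety is the primary objective (7.1), the escalation review in 12.5 lists no IgG data, and no hypothesis test is powered on IgG. What is exposed is the Day 85 immune response, which the plan ranks first among its immunological endpoints.

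**What to change.** Amend 13.1, and mirror the change in the SAP and 15.2:

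- Main analysis: all valid results, on log10 IgG, in the IG set. The outlier-excluded run becomes the sensitivity analysis, with its test, scale, threshold and grouping stated.
- Exclude or replace a value only for a documented assay-run or sample-handling failure, decided blind to treatment as well as to identity, by a named role.
- Unexpected kinetics may still trigger a repeat. Fix in advance which value is reported afterwards, whichever way it moves.
- Keep results confirmed on repeat in the analysis, keep every original value on file, and list all changes.

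The cost is wording, since both runs are already planned. The intervals will be wider. Against raw-scale exclusion the simulated width ratios of 0.93 to 0.88 mean about 8% to 14% wider (1/0.93 = 1.08; 1/0.88 = 1.14). Against log-scale exclusion without non-responders they are about the same. In the most affected case (log scale, SD 0.3, 1 to 3 non-responders at 1.5 log10) they are roughly 30% to 55% wider, depending on how the widths are averaged. That extra width reflects real variation between subjects that exclusion would hide.
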